7.4 Disposition of Subjects

Study information, including the date first subject signed ICF, date of last subject's last visit/contact, date of last subject's last procedure for collection of data for primary endpoint, MedDRA Version, WHO Drug Version, and SAS Version is presented. For screen failure patients, who signed informed consent and were not treated in the study, demographics and the reasons for screen failures will be generated in a summary table.

The disposition includes the number and percentage of patients in the following categories: patients in each of the study populations, primary reason off treatment, ongoing (if applicable at the time of database lock/data cut-off), participating in PFS follow-up, and the primary reason discontinued from the study. This information will be presented by safety analysis set.

7.5 Demographic and Other Baseline Characteristics

All demographics and baseline characteristics will be summarized by safety analysis set.

Demographics

Demographic data to be evaluated will include age, sex, race, ethnicity, height, and weight.

Disease characteristics:

- Type of cancer
- Years since initial diagnosis [(date of the first dose – date of the diagnosis) / 365.25].
- Anatomic stage

- Number of sites of cancer involvement
- Eastern Cooperative Oncology Group (ECOG) performance status.

Prior therapy

- Prior radiation.
- Prior surgery/procedure.
- Prior systemic anti-cancer therapy.
- Lines of prior therapy (descriptive statistics and categorical summary: 0, 1, 2, 3, 4, 5, 6, >6).
- Lines of prior therapy initiated within 12 months of the first dose of the study drug (categorical summary).
- Last line of prior therapy
- Best response at the last line of therapy

7.6 Medical History and Concurrent Medical Conditions

Medical history and concurrent medical conditions will be coded using the latest MedDRA dictionary. Concurrent medical conditions are the ones ongoing or started on or after the day inform consent was signed. Medical history and concurrent medical conditions will be summarized separately by safety analysis set. Medical history and concurrent medical conditions will be listed together along with a flag about whether the medical condition is concurrent or not. If both start date and stop date are missing, medical condition will be assumed to start before inform consent and continue after treatment discontinuation. If only start date is missing, then medical condition will be assumed to start before inform consent. If stop date is missing, then medical condition will be assumed to continue after treatment discontinuation.

7.7 Medication History and Concomitant Medications

Medication history and Concomitant medications will be coded using the latest World Health Organization (WHO) Drug Dictionary. Concomitant medication is defined as the medication ongoing or started on or after the first dose date of the study drug through 30 days after the last dose of the study drug, or the start of subsequent anti-cancer therapy, whichever occurs first. The number and percentage of patients taking concomitant medications will be tabulated by WHO standardized medication name. Medication history will also be summarized. Medication history and concomitant medication will be listed together with the following flags:

1. Discontinued before the first dose date of the study drug.
2. Started on or after dosing.

3. Started after 30 days after the last dose of the study drug, or the start of subsequent anti-cancer therapy, whichever occurs first.

If both start date and stop date are missing, medication will be assumed to start before the first dose date of the study drug and continue after treatment discontinuation. If only start date is missing, then medication will be assumed to start before the first dose date of the study drug. If only stop date is missing, then medication will be assumed to continue after treatment discontinuation.

7.8 Study Drug Exposure and Compliance

Extent of Exposure

The exposure to study drugs (modakafusp alfa and Pembrolizumab) will be characterized by summaries and descriptive statistics of duration of treatment in weeks, number of treated cycles (1, 2, 3, 4, 5, 6, 7-12, >12 and summary statistics), and relative dose intensity will be summarized by safety analysis set.

A treated cycle is defined as a cycle in which any amount of the study drug for at least one of the dosing days in the cycle is given.

Cumulative dose (mg/kg): sum of all doses of the study drug administered to a subject during the treatment period.

Relative dose intensity = (actual dose per week / planned dose per week) × 100. The actual dose per week adjusts for delays in the start of a cycle and assumes the last cycle is fixed at the intended duration.

- Date of last exposure of the study drug = min(date of last dose of the study drug + treatment interval - 1, date of death, start date of the subsequent treatment - 1). This algorithm may be adjusted as appropriate by consulting the study clinician.

Actual dose per week and planned dose per week are calculated as follows:

- Actual dose per week: cumulative dose of the study drug in mg/kg / [(date of the last exposure of the study drug – date of the first dose + 1) / 7].
- Planned dose per week: starting dose of study drug (mg/kg) on C1D1 / treatment interval in weeks.

Action on Study Drug

The reason for dose modification (increased, reduced, interrupted, withdrawn, delayed, drug infusion interrupted, infusion rate increased, infusion rate reduced) of the study drug will be summarized by cycle for the safety analysis set.

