8.0 STUDY DRUG

8.1 Study Drug Administration

All protocol-specific criteria for administration of study drug must be met and documented before drug administration. Study drug will be administered only to eligible patients under the supervision of the investigator or identified subinvestigator(s).

The initial dose should be based on a patient's weight at screening and only adjusted if there is a $\geq 10\%$ change in body weight.

Investigational sites should refer to the pharmacy manual for preparation of each dose. Modakafusp alfa doses < 1.5 mg/kg will be administered over 1 hour (± 10 minutes). Modakafusp alfa doses ≥ 1.5 mg/kg will be administered over 2 hours (± 10 minutes) and could be extended to 4 hours at the investigator's discretion. Any decrease in infusion duration must be discussed with and agreed upon by the sponsor. If a patient presents with an infusion-related reaction at any dose level, the duration of the infusion may be extended per investigator's discretion. Total time from modakafusp alfa dosing solution preparation until end of infusion must not exceed 7 hours.

In the combination treatment cohorts, the recommended pembrolizumab dose of 400 mg will be administered as an IV infusion over 30 ± 10 minutes Q6W in combination with modakafusp alfa. Please see premedication and observation guidelines in Section 8.8.1.

Pembrolizumab will be administered before modakafusp alfa on days when both modakafusp alfa and pembrolizumab are given. At least 30 minutes should elapse between the completion of the infusion of the first study drug and the initiation of the infusion of the second study drug.

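### SAP 7.8 says the last cycle counts at full length, but its formula cuts it at death or new therapy, which biases relative dose intensity upward for those patients

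*SAP*

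**What the plan says.** SAP 7.8 defines RDI as actual dose per week over planned dose per week, times 100, for both modakafusp alfa and pembrolizumab. It describes the intent in words: "The actual dose per week adjusts for delays in the start of a cycle", and it "assumes the last cycle is fixed at the intended duration".

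The bullet that follows defines the date of last exposure as "min(date of last dose of the study drug + treatment interval - 1", or, if earlier, "date of death, start date of the subsequent treatment - 1". It adds: "This algorithm may be adjusted as appropriate by consulting the study clinician".

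Actual dose per week is cumulative dose in mg/kg divided by the weeks from first dose to that date. Cumulative dose is the "sum of all doses of the study drug administered to a subject during the treatment period". Planned dose per week is the Cycle 1 Day 1 dose in mg/kg divided by the full treatment interval. For pembrolizumab, however, Protocol 8.1 says that "the recommended pembrolizumab dose of 400 mg will be administered as an IV infusion", every 6 weeks, so it is a flat dose.

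**The concern.** The sentence and the formula cannot both be followed when death or new therapy falls inside the last interval. In that case the last dose stays whole in the numerator and its interval shrinks in the denominator, so RDI passes 100% although no extra drug was given.

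A value above 100% should mean something in this trial. Protocol 8.6.1 allows dose increases within a patient, and visit windows allow slightly early doses. The artefact cannot be told apart from these in a summary table. In the affected patients it can also offset or reverse the effect of a real delay. Two programmers reading the section could produce different tables. SAP 7.2 calls for means and maxima, which a few extreme values would distort.

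The mg/kg formulas also have no direct input for a drug given as a flat 400 mg.

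**Working it through.** The plan states no RDI value, so there is no figure to reproduce. The check applies the SAP formula directly.

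**Inputs**
- Interval L: 21 days for modakafusp alfa and 42 for pembrolizumab (Protocol 2.0).
- n doses, all at the starting dose D.
- E: exposure days from first dose to date of last exposure, both included (SAP 7.8).
- k: exposure days counted from the last dose, with the dose day as day 1. The documents do not give this. Assumed range: 5 to 20 for modakafusp alfa, 14 to 28 for pembrolizumab.

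**Formula.** Actual dose per week is nD/(E/7) and planned is D/(L/7), so RDI = 100 × nL/E. On schedule, E = (n − 1)L + k. With the last interval fixed, k = L, E = nL and RDI is exactly 100% for any n. Truncation only reduces E, so it can only raise RDI.

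**Modakafusp alfa, on schedule (fixed rule = 100% throughout)**

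| Doses | k=5 | k=7 | k=10 | k=14 | k=20 |
|---|---|---|---|---|---|
| 1 | 420% | 300% | 210% | 150% | 105% |
| 2 | 161.5% | 150% | 135.5% | 120% | 102.4% |
| 6 | 114.5% | 112.5% | 109.6% | 105.9% | 100.8% |
| 12 | 106.8% | 105.9% | 104.6% | 102.9% | 100.4% |

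For example, one dose and k = 14: 100 × 21/14 = 150%. Six doses and k = 5: 100 × 126/(105 + 5) = 114.5%.

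**Pembrolizumab.** One dose: k = 14 gives 300%, k = 21 gives 42/21 = 200%, and k = 28 gives 150%. Two doses with k = 21: 84/63 = 133.3%.

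**A delay offset by truncation.** Doses on Days 1 and 29 (7-day delay), new therapy on Day 43, so exposure ends on Day 42: 100 × 42/42 = 100%. Under the fixed rule exposure ends on Day 49: 100 × 42/49 = 85.7%. With a 14-day delay (Days 1 and 36), the fixed rule gives 42/56 = 75.0%, and truncation at k = 7 gives 42/42 = 100%.

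**A patient who stops early without truncation.** The same doses on Days 1 and 29, treatment then stopped, with the patient alive through Day 49 and no new therapy before Day 50: 85.7% under both rules.

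**Imputed dates.** SAP Appendix B sets the subsequent anticancer therapy start to the day after the last dose of study treatment when the year is missing. It does the same when only the year is usable and matches the last-dose year, or when the first of the recorded month is not after the last dose. If that date enters the formula, exposure ends on the last-dose date itself and k = 1. One modakafusp alfa dose then gives 100 × 21/1 = 2100%, and two on-schedule doses give 100 × 42/22 = 190.9%.

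**The case against.** **Delays are visible elsewhere.** SAP 7.8 summarizes reasons for dose modification by cycle, including delays, and SAP 7.12.1 tabulates adverse events that led to delays, reductions and interruptions. This stands. A reader might infer that the formula hides delays in general. It can offset them only within RDI, and only in truncated patients.

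**Nothing depends on RDI.** It is not an endpoint in SAP 5.1 to 5.3. The recommended phase 2 dose comes from DLTs and the dose-escalation model, or from PK/pharmacodynamic or exposure-response analysis. This stands and keeps the point minor.

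**Large values need unusual timing.** Eligibility requires ECOG 0-1 and life expectancy over 12 weeks. Scheduled scans fall up to 7 days before Day 1 of Cycles 3, 5 and 7. For on-schedule patients, new therapy prompted by such a scan gives at most 120% after two modakafusp alfa doses (42/35) and 105.9% after six (126/119). For one pembrolizumab dose it gives at most 120% (42/35). This is fair for scheduled scans, but scans are also allowed when clinically indicated, and deaths and imputed dates follow no scan schedule.

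**Truncated intervals may be rare.** A reader might infer that they are common from Protocol 4.3.2.2: 70.6% of 17 patients off treatment, mostly for progression, a median of 2 cycles and a median duration of 3.14 weeks. Those figures count treatment stops, not deaths or new therapy inside the interval, and concern single-agent patients only. Neither rarity nor frequency can be shown.

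**The convention is a choice.** With the interval fixed, a patient who dies after one dose scores 100%, which says little about tolerability. That is true, but the SAP's sentence already makes this choice. The discretion clause gives no criteria and does not settle the conflict.

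**The pembrolizumab units are cosmetic.** This is largely right. If the same weight converts both terms it cancels, and Protocol 8.6.3.2 bars changes to the pembrolizumab dose. It is a units correction.

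**Conclusion.** The contradiction and the direction of the bias are certain from the text of SAP 7.8. The size depends on the number of doses and on the timing of the event, which is assumed here. Over 5 to 20 exposure days from the last modakafusp alfa dose, RDI runs from 105% to 420% after one dose and from about 102% to 162% after two. From six cycles on, the excess runs from under 1 to about 15 points. The 2100% case requires that a date imputed under Appendix B feed the formula, which the SAP neither states nor rules out.

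A reader might infer that early stopping in itself inflates RDI. The formula does not do that: only death or new therapy inside the last interval truncates it. The documents also do not support saying that tolerability as a whole will look better than it is, because the number of affected patients is unknown and ORR and DLTs are untouched. The point is minor but worth correcting, because the written rule gives a wrong result.

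**What to change.** In SAP 7.8, end exposure for RDI at date of last dose plus treatment interval minus 1, without the death and subsequent-treatment terms. This follows the SAP's own sentence and keeps imputed therapy dates out of the calculation. Keep the truncated date for treatment duration only, and say so.

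For pembrolizumab, express cumulative, actual and planned dose in mg (400 mg per 6 weeks, or the regimen assigned).

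Deleting the sentence about the fixed last cycle and declaring the truncation would also remove the contradiction. It would leave the upward bias, because planned dose per week would still use the full interval.

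The cost is about a line of SAP text and a small programming change. No new data are needed.

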8.6 Dose Modification Guidelines

8.6.1 Inpatient Dose Escalation

Patients who have tolerated treatment with modakafusp alfa well at the initially assigned dose may be allowed to increase their doses of modakafusp alfa in subsequent cycles of treatment following sponsor and investigator review of the available data. Inpatient dose escalation will be permitted only after all patients in the next higher dose level cohort have completed assessments for Cycle 1 and a decision has been made that this dose level does not exceed the MTD.

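### For patients who escalate modakafusp alfa, relative dose intensity does not measure delivery of the planned dose, because SAP 7.8 keeps the Cycle 1 Day 1 dose as the denominator throughout

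*SAP*

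**What the plan says.** SAP section 7.8 (Study Drug Exposure and Compliance) defines "Relative dose intensity = (actual dose per week / planned dose per week) × 100". The two parts are built as follows.

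- **Numerator.** Cumulative dose is the "sum of all doses of the study drug administered to a subject during the treatment period", divided by the weeks from first dose to last exposure. Last exposure is the last dose date plus the treatment interval minus one day, cut short by death or by a subsequent treatment. The SAP adds: "The actual dose per week adjusts for delays in the start of a cycle and assumes the last cycle is fixed at the intended duration".
- **Denominator.** "Planned dose per week: starting dose of study drug (mg/kg) on C1D1 / treatment interval in weeks". This is one value per patient for the whole treatment period.

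Protocol section 8.6.1 says: "Patients who have tolerated treatment with modakafusp alfa well at the initially assigned dose may be allowed to increase their doses of modakafusp alfa". It attaches a condition: "Inpatient dose escalation will be permitted only after all patients in the next higher dose level cohort have completed assessments for Cycle 1". That level must also have been judged not to exceed the MTD.

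The SAP foresees such patients. Section 7.8 lists increases among the dose modifications to be summarised, and section 7.12.1 mentions patients later treated above their original level. It does not reset the denominator, cap RDI or separate escalated patients.

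Section 7.8 applies its exposure summaries to both drugs but writes the dose quantities in mg/kg. For pembrolizumab, protocol section 8.1 says "the recommended pembrolizumab dose of 400 mg will be administered as an IV infusion", and section 8.6.3.2 does not allow that dose to be modified.

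**The concern.** RDI is normally read as the share of the planned dose that the patient received on schedule, with 100% meaning full delivery. Once a patient escalates, the SAP's numerator follows the new dose and its denominator follows the old one. The ratio then mixes two things: how far the dose was raised, and how well the schedule was kept. A value above 100% can go with substantial delay.

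Phase 1b exposure is presented by dose level, in cohorts that start at about 3 patients. At that size one escalated patient can lift a dose-level mean above 100% while the others fell clearly short. Tolerability is the phase 1b primary objective, so an exposure table that reads as full delivery when delivery was incomplete is unhelpful, even though RDI is not itself an endpoint.

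The unit problem for pembrolizumab is separate and smaller: a flat dose is being described by a weight-based formula.

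**Working it through.** The SAP states no RDI value, so there is no figure of the plan's to reproduce. The check applies its formula to illustrative histories.

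**Inputs from the documents.** Dose levels are 0.1, 0.2, 0.4, 0.75, 1.5, 3 and 6 mg/kg in 21-day cycles (protocol section 2.0), so one step multiplies the dose by 2.0, or by 1.875 from 0.4 to 0.75. A cycle is delayed in 1-week units (protocol section 8.6.2).

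**Assumptions.** Six cycles; the dose and delay histories below; no death or new therapy cutting the last cycle short.

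**Formulas.**
- SAP: RDI = (sum of doses / actual weeks) / (C1D1 dose / 3) × 100.
- Against assigned dose: (sum of doses / actual weeks) / (sum of assigned doses / planned weeks) × 100.

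**Patients who do not escalate**
- Constant dose, no delay: 100% by both formulas.
- Constant 0.1 mg/kg, four 1-week delays: 18/22 = 81.8% by both.
- 0.2 mg/kg for 2 cycles, then reduced to 0.1 for 4: 0.8/1.2 = 66.7% by both.

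The SAP formula works for these patients.

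**Escalation at Cycle 3** (0.1 mg/kg × 2, then 0.2 mg/kg × 4)
- Total dose: 2 × 0.1 + 4 × 0.2 = 1.0 mg/kg.
- No delay, 18 weeks: SAP planned total is 18 × 0.1/3 = 0.6, so RDI = 1.0/0.6 = 166.7%. Against assigned dose it is 100%.
- Cycles 3 to 5 each running 28 days: 6 + 12 + 3 = 21 weeks. SAP planned total is 21 × 0.1/3 = 0.7, so RDI = 1.0/0.7 = 142.9%. Against assigned dose: (1.0/21)/(1.0/18) = 18/21 = 85.7%.
- Reduced back to 0.1 mg/kg for Cycles 5 and 6, no delay: total dose 0.8. SAP RDI = 0.8/0.6 = 133.3%. Against assigned dose: 0.8/1.0 = 80.0%.
- Delay needed before the undelayed 166.7% falls to 100%: 1.0/(0.1/3) = 30 weeks, so 30 − 18 = 12 weeks (84 days) on a planned 126 days.

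For the 0.4 to 0.75 step, the no-delay value is (0.8 + 3.0)/2.4 = 158.3%.

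**Late escalation** (0.1 mg/kg × 5, then 0.2 mg/kg × 1)
- No delay: 0.7/0.6 = 116.7%.
- Four 1-week delays, 22 weeks: 0.7/(22 × 0.1/3) = 95.5%, against 18/22 = 81.8% of the assigned dose. The inflation is much smaller.

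**Effect on a small mean** (illustration, grouping by starting dose level). Two non-escalated patients at 81.8% and one undelayed escalated patient at 166.7%: (81.8 + 81.8 + 166.7)/3 = 110.1%. Against assigned dose: (81.8 + 81.8 + 100)/3 = 87.9%.

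**The case against.** The strongest reply is that measuring intensity against the initially assigned dose is a disclosed and reproducible definition, and that a value above 100% itself signals escalation. No decision depends on it either: RDI is not an endpoint, MTD decisions use DLTs, and tolerability is judged from TEAEs, SAEs, DLTs and TEAEs leading to modification. This stands as a limit on importance. It does not rescue the measure, because a reader given 143% cannot tell full delivery after escalation from 86% delivery.

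Three stronger readings are tempting, and the documents do not support them.

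- **That delays and reductions are concealed.** Delays still lower the value in proportion: 166.7% to 142.9% is the same relative fall as 100% to 85.7%. SAP 7.8 also summarises the reasons for dose modification by cycle, section 7.12.1 tabulates TEAEs resulting in delays and in reductions, and Appendix A lists exposure and TEAEs resulting in dose modification by patient. What is lost is the meaning of the RDI level, not the record of delays.
- **That escalated patients are treated longest and dominate the averages.** The documents give neither their number nor their duration of treatment. Escalation waits for the next cohort to complete Cycle 1, and at the January 2021 cutoff the median was 2 cycles and 70.6% had stopped treatment. There may be few such patients. Medians and ranges are reported as well as means.
- **That weight loss inflates pembrolizumab RDI.** A 9% loss would make an unchanged dose count as 1/0.91 = 110% in mg/kg, but only if current weight were used, which the SAP does not say. That figure is also a ratio for a single dose, not an RDI. With one fixed weight, the weight cancels.

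**Conclusion.** The point holds for patients whose modakafusp alfa dose is escalated. Because the escalation rule refers to a next higher dose cohort, these are mainly phase 1b patients (about 30 of up to 114 planned). For a one-step escalation at Cycle 3 of 6, the SAP formula multiplies the share of assigned dose delivered by 1.0/0.6 = 1.67 (1.58 for the 0.4 to 0.75 step). Later escalation inflates it less. These sizes rest on assumed dose histories; the effect on the trial's actual summaries cannot be calculated, because the number escalated is not given.

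For pembrolizumab, what stands is a unit mismatch: a mg/kg formula for a flat dose. No bias can be shown from it.

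Severity is low. It is worth correcting because it is cheap, but no endpoint or dose decision depends on it.

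**What to change.** In SAP 7.8, replace the planned dose per week with:

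- **Planned cumulative dose** = the sum over cycles of the assigned dose. The assigned dose is the starting level, raised from the cycle at which an approved escalation takes effect, and not lowered for toxicity reductions, so that reductions still count as shortfall.
- **Planned time** = number of cycles × treatment interval.
- **Planned dose per week** = planned cumulative dose / planned time.

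If the present definition is kept, report RDI separately for patients who escalated and state that their values are relative to the starting dose.

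For pembrolizumab, compute cumulative dose, planned dose and RDI in mg, with the interval of the assigned regimen.

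The cost is SAP wording and minor programming on dosing data already collected. RDI values for escalated patients will become less favourable; those for other patients do not change.
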